Thermotape High-adhesion Medical Tape Comparison Study

June 21, 2022

Background:

Currently, modern medical tapes can be classified into two categories, high-adhesion tape, and low-adhesion tape. Both tapes, however, are not sufficient for use in a medical environment; high-adhesion tape, when removed, can cause medical adhesive related skin injuries (MARSI), which is liable to cause patients to have to return to the hospital to treat it, resulting in a dramatic increase in medical expenses once fully recovered. Conversely, low-adhesion tape is ill-suited for securing medical devices, such as IV lines, in place because of having low adhesion. As a result, a patient's ability to recover is impacted, overall increase medical expenses from an extended stay at the hospital.

Thermotape is designed to combat both flaws, by acting as a high-adhesion tape until heated, where it can be removed as easily as low-adhesion tape.

Objective:

This objective of this study is to compare the safety and performance of Thermotape compared to Tegaderm™ tape and Kind™ tape over the course of 24 hours. In regard to safety, pain inflicted during removal and any potential effects will be monitored for Thermotape versus Tegaderm™ and Kind™ tape.

Design:

A single blinded comparative clinical study, where researchers will know the tape being applied while the subjects do not.

Methods:

Consent will be obtained from the subject as they enter the building for tape application. This will be done by providing a paper consent form detailing the necessary details concerning the trial. If consent is obtained, they will be allowed into the room for tape application.

Before tape application, both forearms will be cleaned using an isopropyl alcohol wipe and skin markers will be used to draw lines, with two inches of spacing between, to separate areas of tape application. The marks began at the elbow and continued down the forearm. Following the pre-tape preparations process, Thermotape, Kind™ tape, and Tegaderm™ tape will be applied horizontally, in vertical

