succession. Following Thermotape's application, a finger will be used to rub Thermotape in a vertical motion to ensure that the tape, especially edges, are fully adhered. The same procedure will be used for Kind™, however Tegaderm™ will not require the same adhesion procedure, as noted by a nurse practitioner. The tapes will be applied in a random order. Once all tapes are applied, researchers will give the following speech: "Now that the tapes have been applied, please do not do any physically extraneous activities, like swimming in the ocean, running a marathon, or storm chasing. Basically, any activities that make you sweat. Additionally, please do not shower until we remove the tapes, even if you really want to. If you do end up getting the tapes wet, through sweat or by showering, please note it down in the activity log on the back of your activity log. Also, try not to pick at the tapes, even if the corners start lifting. Thank you and we'll see you back tomorrow!" The speech requests that subjects are to not participate in strenuous physical activity or shower for the duration of the 24-hour study. One researcher is to apply the tape to the participants. Each tape will be cut 1 inch wide by 2 inches long.

When subjects return for tape removal, they will be given a pain survey, with a 0-to-10 Wong-Baker scale, to fill out after each piece of tape is removed. One photo will also be taken of the forearms to document the state of the subject's forearms 15 minutes after tape removal. Each piece of tape is then to be analyzed for wear using a 0-to-7 point scale.

When removing the tapes, an edge will first be lifted and then it will be peeled at an angle of 180° at a consistent rate. If a hair is encountered, the tape will be removed following the root of the hair to its tip. After the removal of each piece of tape, it will be placed on a glass slide and taped down for later quantification of cell and hair counting caused by tape removal. No gloves will be used throughout the process. During removal, if a subject shows signs of extreme discomfort or the skin appears to start tearing, manual removal will be stopped and a commercial silicon-based remover, Brava, will be used to remove the tape instead. To do so, Brava will be rubbed all over the tape, including the edges, and under the skin after removal of the tape. Gloves will be used in the case of using Brava to remove tape.

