Removal of tape from both forearms will stay consistent, however one forearm (left), will use a Dynarex heat pack to assist in tape removal. Prior to heat pack activation, a corner for each tape sample will be lifted. After, the heat pack will be activated and kneaded for one minute before application onto the subject's skin. Then, the heat pack will be folded in half and applied to each piece of tape for 30 seconds before removal. The heat pack will be kneaded for 20 seconds between each tape removal.

Following the removal of all pieces of tape, the pain survey is collected, and each subject will be asked to wait 15 minutes following removal to examine for any redness that may have occurred. A 0-to-4 point scale will then be used to assess for erythema present on the forearms.

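### Heat goes to the left forearm in every subject, so the effect of heat cannot be separated from a left-right difference

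*Protocol*

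**What the plan says.** The Methods section of the protocol prepares both forearms and says that "Thermotape, Kind™ tape, and Tegaderm™ tape will be applied horizontally, in vertical" succession. The natural reading, though it is not spelled out, is one set of three tapes on each forearm. The only randomisation is of position: "The tapes will be applied in a random order".

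For removal, the protocol says "Removal of tape from both forearms will stay consistent", with one difference: "one forearm (left), will use a Dynarex heat pack to assist in tape removal". Every strip on that forearm is heated, comparators included: "the heat pack will be folded in half and applied to each piece of tape for 30 seconds before removal". No exception to the left side is given, and nothing alternates, balances or adjusts for side. The order in which the two forearms are removed is not stated.

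Pain is scored after each strip. Redness is read once at the end: "each subject will be asked to wait 15 minutes following removal to examine for any redness that may have occurred". The photographic record is also shared: "One photo will also be taken of the forearms".

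The SAP lists pain and skin irritation as its primary results and plans an average for each group. The SAP text available for review contains no model, no test, no term for side or handedness, and no named comparison between forearms.

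**The concern.** The Background section describes Thermotape as working "by acting as a high-adhesion tape until heated, where it can be removed as easily as low-adhesion tape". The direct ways to examine that claim are to compare Thermotape removed with and without heat, and to compare heated Thermotape with a comparator removed in the ordinary way. Both cross from the left forearm to the right. If the forearms differ for any reason other than heat, that difference is credited to heat, and a larger sample only makes the wrong answer look more precise.

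Forearm order could add a second confounder. If most subjects have the same forearm done first, heat is also tied to the place in the sequence of pain ratings and to the time that redness has had to fade before the single reading.

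**Working it through.** The plan states no sample size, SD, effect size or significance level, so there is no figure of its own to reproduce. The check has three parts.

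**1. Can the contrasts be estimated?** Take a linear model with subject, tape (three levels), heat, tape-by-heat and side. For 20 illustrative subjects, two forearms and three tapes, the columns are 20 + 2 + 1 + 2 + 1 = 26. Allowing the side effect to differ by tape adds 2, giving 28. The aliasing does not depend on the number of subjects.

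| Design | Rank, same side effect for all tapes | Rank, side effect differs by tape |
|---|---|---|
| Heat always left | 25 of 26 | 25 of 28 |
| Heated side balanced | 26 of 26 | 28 of 28 |

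| Contrast, heat always left | Same side effect for all tapes | Side effect differs by tape |
|---|---|---|
| Heated minus unheated, same tape | not estimable | not estimable |
| Heated Thermotape vs unheated comparator | not estimable | not estimable |
| Heated Thermotape vs heated comparator (left arm) | estimable | not estimable |
| Tape-by-heat interaction | estimable | not estimable |
| Unheated Thermotape vs unheated comparator (right arm) | estimable | estimable |

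With the heated side balanced, all five are estimable in both models.

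**2. What would a side effect do?** With heat always left, the expected heated-minus-unheated difference is the heat effect plus the side effect, so the bias equals the side effect at any sample size. For illustration, assume no true heat effect, an SD of 2 points for the paired left-right pain difference, and a two-sided 5% paired t-test. The noncentrality is δ√n / 2; for δ = 0.5 and n = 20 it is 0.5 × 4.47 / 2 = 1.12.

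| Assumed side effect δ | n = 20 | n = 30 | n = 50 |
|---|---|---|---|
| 0.25 | 8.3% | 10.2% | 13.9% |
| 0.5 | 18.6% | 26.3% | 41.0% |
| 1.0 | 56.5% | 75.4% | 93.4% |

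In simulation at δ = 0.5 (10,000 trials), fixed-left heat gave a bias of 0.50 and rejection in 19.7%, 26.3% and 41.1%. With the heated arm randomised 1:1 and side in the model, the bias was 0.00 to 0.01 and rejection 5.0%, 4.9% and 5.0%. The interaction was rejected in 4.9%, 5.2% and 4.9% under fixed-left heat with a side effect common to all tapes.

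Relying on the interaction has a price. Against one comparator its variance, relative to the single-tape heat contrast, is 2(1 − ρ), where ρ is the correlation between the two tapes' left-right differences: 2.0 at ρ = 0, 1.5 at 0.25 and 1.0 at 0.5. It is also not immune. If the 0.5-point side effect acts on one tape only and ρ = 0, the SD becomes 2√2 = 2.83 and the false-positive rates are 11.7%, 15.5% and 23.2%.

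**3. Erythema timing.** The protocol gives 60 s of kneading at the start, 30 s of heat per strip and 20 s of kneading between strips. Assume r = 30 to 90 s for each removal and pain rating, and the same forearm order throughout. Counted from the start of that forearm's procedure, unheated strips come off at r, 2r and 3r (mean 2r). Heated strips come off at r + 90, 2r + 140 and 3r + 190 (mean 2r + 140).

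- Unheated forearm first: mean gap = (3r + 2r + 140) − 2r = 3r + 140 = 230 to 410 s (3.8 to 6.8 min).
- Heated forearm first: mean gap = (3r + 190 + 2r) − (2r + 140) = 3r + 50 = 140 to 320 s (2.3 to 5.3 min), in the opposite direction.
- Separate clock for each forearm, started at its last strip: (r + 50) − r = 50 s in either order.

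**The case against.** The strongest reply is that the affected contrasts are not shown to be planned. The Objective compares Thermotape with the two commercial tapes. Because every left-arm strip is heated, that can be done within a forearm: heated against heated, unheated against unheated. This stands as a limit on the concern; the case for the cross-arm contrasts rests on the product claim in the Background. But the SAP's group averages do not rule them out, and setting heated and unheated averages side by side makes the confounded comparison.

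Second, no left-right difference is documented, and the SD, sample sizes and side effects above are all assumed. The SAP text plans no test, so the false-positive rates describe an analysis it does not contain. This too stands. What is certain is the aliasing, and that the bias equals the side effect, whatever that is.

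Third, forearm order is unspecified, so the timing problem is conditional, and nothing in the documents shows that a few minutes changes a redness grade. This is right, and the timing point is secondary.

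Fourth, subjects can feel the heat pack, and the blinding concerns only which tape is applied. Randomising the side removes the side bias, not any effect of expectation on reported pain.

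**Conclusion.** The concern holds. As written, heated versus unheated removal of a given tape, and heated Thermotape versus a comparator removed without heat, are fully aliased with arm side for both primary outcomes. That follows from the text, provided that the left-arm rule applies to every subject, as its wording implies.

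The size of the bias is unknown. On the stated assumptions, false-positive rates run from 8% (0.25 points, 20 subjects) to 93% (1 point, 50 subjects).

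The right-arm tape comparison is sound in either model. The left-arm tape comparison and the interaction are sound only if the side effect is the same for all tapes, which is not assured on bounded 0-to-10 and 0-to-4 scales. Even then they answer a narrower question: whether tapes differ under one condition, or whether heat helps one tape more than another. They do not give the absolute effect of heat. The point should be fixed, chiefly because it bears on the product claim and the remedy is cheap.

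**What to change.** **Essential.** Randomise 1:1, from a balanced list, which forearm of each subject gets the heat pack, and record it. State in the SAP that heated and unheated removal are compared within subject, with side as a model term.

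**Worth adding.** Randomise and record which forearm is removed first. Start the 15-minute erythema clock separately for each forearm at its last strip, with its own reading and photo. On the timing assumptions above, the two readings fall 3r = 90 to 270 s apart (heated first) or 3r + 190 = 280 to 460 s apart (unheated first), that is 1.5 to 7.7 min. Both come after all strips are off, so one assessor can do both and the visit is no longer. Using the same tape order on both forearms is an optional gain in precision.

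**If left-only heat is kept.** Report same-arm tape comparisons and the tape-by-heat interaction as the interpretable results. State that the left-arm comparison and the interaction assume a side effect common to all tapes. Label any cross-arm difference as *left heated versus right unheated*.

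**Cost.** An allocation list, two form fields, a second timed reading and photo per subject, and short edits to the protocol and SAP. No extra subjects, staff or visits. The essential part alone needs only the list, one field and the edits.

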## Primary Results:

### Pain experienced from Removal

The following 0-to-10-point Wong Baker scale will be used to quantify pain experienced by the subject during tape removal:

Subjects are to use the scale to determine the level of pain experienced after each piece of tape is removed and researchers are to record the number determined. Whole numbers between each face may be used as well.

The average for each population group will be obtained after data has been collected from the participants.

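### All three tapes are peeled with heat on one arm and without it on the other, but the visible SAP does not use the heated comparators as the control for heat

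*Protocol*

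**What the plan says.** **Product idea.** The Protocol's Background describes Thermotape as working "by acting as a high-adhesion tape until heated, where it can be removed as easily as low-adhesion tape". The Objective is a comparison of Thermotape with the two other tapes on safety and performance; it does not name heat.

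**Design.** In the Protocol's Methods both forearms are prepared and tape is removed from both. Three tapes are used ("Thermotape, Kind™ tape, and Tegaderm™ tape will be applied horizontally, in vertical" succession), and "The tapes will be applied in a random order". At removal, "one forearm (left), will use a Dynarex heat pack to assist in tape removal", and the pack is used on every strip of that arm: "Then, the heat pack will be folded in half and applied to each piece of tape for 30 seconds before removal". I read this as all three tapes on each arm, heated on the left and unheated on the other. Pain is scored after each strip, and each removed strip goes on a slide for cell and hair counts.

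**Analysis.** For pain the SAP says: "The average for each population group will be obtained after data has been collected from the participants". Erythema and skin cells are handled the same way, and the population group is not defined. Hair and trans-epidermal water loss are averaged by brand, with no mention of arm. Tape wear is also averaged by brand, but the SAP grades it when subjects come in for removal, so it is left aside here. No section of the SAP text available mentions heated removal or sets out a test, model, interval or contrast. A figure and a stretch of SAP text are not available, so this describes the visible text only.

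**The concern.** The property that sets Thermotape apart is a change on heating. Heating the comparators as well gives the study a control for what heat does to any adhesive, or to any subject's rating. The visible analysis never uses that control.

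Two opposite errors are then open. Heated Thermotape could be compared with unheated Thermotape alone. An easing shared by every tape would then look like a heat switch, and because heat is always on the left, any side or handling effect would be mixed in. Alternatively, averaging by brand across arms blends heated and unheated strips and dilutes an effect that exists only on the heated arm. In neither case does the reported number answer whether heat acts on Thermotape in particular.

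**Working it through.** The visible documents give no sample size, effect size or standard deviation, so there is no figure to reproduce. All numerical values below are assumptions chosen to show direction and size.

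**1. What each comparison measures.** Let mean pain be b (a tape's unheated level), minus h if the strip is heated (easing common to all tapes), minus a further s if it is heated Thermotape. Let a be an additive left-arm effect. T is Thermotape and C is one comparator.

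- T heated − T unheated = −h − s + a
- T heated − C heated = (b_T − b_C) − s
- Brand averages pooled over arms, T − C = (b_T − b_C) − s/2
- Tape-by-heat contrast, (T heated − T unheated) − (C heated − C unheated) = (−h − s + a) − (−h + a) = −s

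Only the last isolates s whatever h, a and the unheated levels are.

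**2. Numbers.** Take unheated levels of 5 for both Thermotape and Tegaderm, and a = 0.

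| Comparison | h=1, s=0 | h=0, s=1 | h=1, s=1 |
|---|---|---|---|
| T heated − T unheated | −1 | −1 | −2 |
| T heated − Tegaderm unheated | −1 | −1 | −2 |
| T heated − Tegaderm heated | 0 | −1 | −1 |
| Pooled brand averages, T − Tegaderm | 0 | −0.5 | −0.5 |
| Tape-by-heat contrast | 0 | −1 | −1 |

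The first two rows give −1 both when there is no Thermotape-specific effect and when the whole effect is specific. The pooled row credits nothing falsely but halves s.

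**3. Precision.** With equal variance σ² and a common correlation ρ among a subject's readings:

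- simple paired difference: 2σ²(1 − ρ)
- contrast against one comparator: 4σ²(1 − ρ), standard error ratio √2 = 1.41
- contrast against the mean of both comparators: 3σ²(1 − ρ), ratio √1.5 = 1.22

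For a 1-point effect, two-sided 5% and 80% power, n = (1.960 + 0.842)² × variance = 7.85 × variance:

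- SD 1.5, ρ 0.7: simple 7.85 × 1.35 = 10.6, so 11; contrast 7.85 × 2.70 = 21.2, so 22
- SD 2.5, ρ 0.3: simple 7.85 × 8.75 = 68.7, so 69; contrast 7.85 × 17.5 = 137.4, so 138

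Over SD 1.5 to 2.5 and ρ 0.3 to 0.7, the contrast therefore needs about 22 to 138 subjects, against 11 to 69 for a simple difference of the same size.

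**4. Limit of the contrast.** Pain is scored 0 to 10. Suppose heat lowers every score by 40%. Thermotape goes from 5 to 3, and a gentle comparator from 1 to 0.6. The contrast is −2 − (−0.4) = −1.6, although heat acted in the same proportion on both.

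**The case against.** The strongest reply is that the stated Objective is tape against tape. The heat switch is a design description in the Background, not a hypothesis, and its wording concerns how easily heated Thermotape comes off relative to another tape. That is a question about level, which the tape-by-heat contrast does not answer. If the undefined population group means tape by arm, the six averages would show the comparators' easing and the contrast would be a subtraction. Much of the problem would then be that groups and comparisons are unspecified in general.

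Most of this stands, and it limits the point. A reader might infer that a shared easing from heat would, under this plan, be credited to Thermotape. The documents do not support that: they plan neither heated against unheated Thermotape nor heated Thermotape against unheated comparators. In a same-arm or pooled tape comparison a common heat effect cancels.

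A reader might also infer that the contrast alone should decide any claim of heat release. It should not, because on a bounded scale a proportional heat effect can produce a non-zero contrast.

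The reply does not remove the point. Nothing visible defines the groups as tape by arm. The by-brand averages, as written, mix the arms. Even six cell means would come without a prespecified difference or interval.

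**Conclusion.** The point holds as a gap in the analysis with a risk in either direction. The visible SAP does not use the heated comparators as the control for heat, although the design supplies them. A common effect of heat or of the left-arm procedure could be credited to Thermotape if its two arms are compared alone; with a common easing of 1 point, the whole apparent effect of 1 point would be spurious. Brand averages pooled over arms, which is how the hair section reads, would report half of a true Thermotape-specific effect.

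This rests on reading the Methods as three tapes on each arm, on an additive model for the sizes given, and on the SAP text available. Direct same-arm comparisons of the tapes remain usable.

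**What to change.** Revise the SAP sections on pain, skin cells and hair to report results by tape and arm, not pooled over arms. Include erythema if it is graded per tape site: the Protocol speaks of grading the forearms and taking one photo of them, so a grade per strip is not established. Water loss is not listed because its section states neither the time nor the arm of the readings.

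For each outcome, give per-subject paired differences with 95% confidence intervals for:

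- (a) heated Thermotape against each heated comparator, and unheated Thermotape against each unheated comparator;
- (b) the contrast (Thermotape heated − unheated) − (comparator heated − unheated), for each comparator.

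Support any statement that heat specifically releases Thermotape with (b), read beside (a) and the six cell means, because the scores are bounded and heat may not act additively. Flag strips switched to the silicone-based remover, since their values may not be comparable with a completed manual peel.

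For pain, skin cells and hair the per-strip data are already planned, so this is analysis wording plus that flag; no change to procedures or enrolment is asked for. The price is precision. Against one comparator, the standard error of (b) is about 1.41 times that of a simple paired difference, or about twice the subjects for the same precision, under equal variance and a common correlation. The interval for (b) may therefore be wide, and should be reported as it is.

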[figure not shown]

## Primary Results:

### Pain experienced from Removal

The following 0-to-10-point Wong Baker scale will be used to quantify pain experienced by the subject during tape removal:

Subjects are to use the scale to determine the level of pain experienced after each piece of tape is removed and researchers are to record the number determined. Whole numbers between each face may be used as well.

The average for each population group will be obtained after data has been collected from the participants.

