### Skin Irritation

The following 0-to-4-point scale will be used to quantify the redness of the skin after tape removal:

Grade	Erythema/Irritation
0	None - natural skin tone
1	Slight - Barely visible increase in pink coloration
2	Mild - Visible increase in light pink coloration
3	Moderate - Diffuse pink coloration, localized or diffuse areas of reddened skin
4	Severe - Intense redness, diffused or localized

The average for each population group will be obtained after data has been collected from participants.

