### Tape Wear

The following 0-to-7-point scale will be used to examine the wear of the tape when subjects come in for tape removal:

Grade	Wear/Adhesion Description
0	Test strip off
1	Test strip almost off
2	$\frac{3}{4}$ of test strip off
3	$\frac{1}{2}$ of test strip off
4	$\frac{1}{4}$ of test strip off
5	3 to 4 edges lifted
6	1 to 2 edges lifted
7	All corners adhered

An average will be taken for the tapes to determine how much wear is experienced for tape brand. An activity log will also be collected from each participant to determine the probable cause of tape wear if a grade three or below are obtained.

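### Each subject appears to wear all three tapes on both forearms, but the available SAP outcome sections plan only averages, with no within-subject contrast and no measure of uncertainty

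*SAP*

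**What the plan says.** The Protocol's Objective is to "compare the safety and performance of Thermotape compared to Tegaderm™ tape and Kind™ tape". Under Methods, "both forearms will be cleaned using an isopropyl alcohol wipe", and then "Thermotape, Kind™ tape, and Tegaderm™ tape will be applied horizontally, in vertical" succession. The order of the tapes is random. On removal: "Removal of tape from both forearms will stay consistent, however one forearm (left), will use a Dynarex heat pack to assist in tape removal". On that arm, "the heat pack will be folded in half and applied to each piece of tape for 30 seconds before removal". Pain is scored after each strip comes off.

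For the first primary outcome, the SAP (Pain experienced from Removal) plans this analysis: "The average for each population group will be obtained after data has been collected from the participants". For the second (Skin Irritation) it plans the same: "The average for each population group will be obtained after data has been collected from participants". Among the secondary outcomes, Tape Wear states: "An average will be taken for the tapes to determine how much wear is experienced for tape brand". Skin Cells, Hair Follicles and Trans-epidermal Water Loss (TEWL) likewise end with an average, by group or by brand. The term for the groups is not defined. The available text gives no number of subjects, SD, significance level or target difference.

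**The concern.** The objective is comparative, and the design is well suited to it because each person acts as their own control. People differ in how they rate pain, in their skin and in their hair. Those differences drop out when two tapes are compared on the same person. The analysis as written neither uses that feature nor attaches any uncertainty to the comparison.

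Two things are at stake. First, a reader given one average per tape has no means of judging whether a gap between them exceeds what chance produces. Second, the wear scale foresees strips that have come off before the return visit, and such a strip may have no removal pain score. The average for one brand may then rest on a different set of people from the average for another.

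The undefined groups add a further ambiguity. If a group means a brand, the heated and unheated arms are pooled, which mixes two removal conditions. Heat is the mechanism by which Thermotape is meant to release, so pooling would blur the effect of interest.

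**Working it through.** **Step 1: the design.** No single sentence says that all three tapes go on both forearms. The inference rests on four statements in the Protocol's Methods: both forearms are prepared, three tapes are applied in succession, tape is removed from both forearms, and the heat pack is used on each strip of the left arm. That gives 3 tapes × 2 arms = 6 conditions per subject. The random order concerns the sequence of tapes, not the assignment of people to separate groups.

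**Step 2: the analysis statements.** All six available outcome sections were compared with that design: pain, irritation, cells, wear, hairs and TEWL. Each states an average. None states a difference within a subject, a model, a test, an SD, a standard error or an interval.

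**Step 3: what averaging loses.** If every subject has a score for tapes A and B, mean(A) − mean(B) = mean(A − B). The point estimate is the same either way, and what is missing is its standard error. If some scores are missing, the two means run over different people and the identity fails.

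**Step 4: size of a chance gap.** The documents give no figure to reproduce, so the inputs here are assumptions: SD of a single pain score 2.0, and within-subject correlation r of 0.3, 0.5 or 0.7.

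- SD of the paired difference = 2.0 × √(2(1 − r)) = 2.37, 2.00 or 1.55.
- Standard error = that SD / √n.
- With no true difference, P(gap ≥ 0.5 in either direction) = 2 × [1 − Φ(0.5 / SE)].
- 95% interval half-width = 1.96 × SE.

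For SD 2.00 and n = 20: SE = 2.00 / √20 = 0.447; 0.5 / 0.447 = 1.118; probability = 0.264; half-width = 0.88.

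Each cell gives the probability of a gap of at least 0.5 points, then the 95% half-width in points:

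| Subjects | SD of difference 2.37 (r = 0.3) | 2.00 (r = 0.5) | 1.55 (r = 0.7) |
|---|---|---|---|
| 10 | 0.50; 1.47 | 0.43; 1.24 | 0.31; 0.96 |
| 20 | 0.35; 1.04 | 0.26; 0.88 | 0.15; 0.68 |
| 30 | 0.25; 0.85 | 0.17; 0.72 | 0.08; 0.55 |
| 50 | 0.14; 0.66 | 0.08; 0.55 | 0.02; 0.43 |

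These use a normal approximation to a whole-number scale, so they are a guide to size only.

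**Step 5: number of primary contrasts.** Two comparators × two heat conditions × two primary outcomes = 8. If these were eight independent tests at 0.05, the chance of at least one false positive would be 1 − 0.95⁸ = 0.34. They are not independent, so this is only indicative, but it shows why an order or an adjustment is needed once intervals or tests are added.

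**The case against.** The strongest reply is that nothing is lost for good. Scores are recorded per strip, so a paired analysis remains possible, and with complete data the averages already give the correct point difference. The available text also states no hypothesis test or success criterion. All of that stands. It does not rescue the plan as written, because averages alone leave the comparative objective unanswered, and choosing the method after seeing the data is what an SAP is meant to prevent.

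Some SAP material ahead of Primary Results was removed and a figure is not shown. It therefore cannot be said that the whole SAP lacks a measure of uncertainty. What can be said is that each available outcome section states its own analysis and none points to a further method.

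Several stronger readings are tempting, but the documents do not support them:

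- *The SAP's groups do not exist.* The term is only undefined. Read as tape by heat condition, it is coherent, though oddly named.
- *The plan will use error bars of the wrong width.* It states none, neither group by group nor strip by strip. Nor would treating one person's two strips of a brand as independent always understate the error. One strip is heated, and if heat shifts the mean by d SD, the true standard error is √((1 + r)/(1 + d²/4)) times the naive one. At an assumed d = 1.5 that is 0.91, 0.98 or 1.04 for r = 0.3, 0.5 or 0.7, so the direction can reverse.
- *Lost strips will bias the pain averages by a known amount.* No passage links strip loss to pain. If loss did depend on a tape's own score, using only complete pairs would cure it only in part. For wear, a strip that has come off is an observed grade of 0, not a missing value.

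**Conclusion.** The point holds for the available text. A design that appears to be fully within-subject is matched with averages alone, for both primary outcomes and all four secondary ones. Following the plan as written would give no interval for the comparison that is its stated purpose.

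The sizes rest on an assumed SD of 2 for paired pain differences. On that basis a gap of half a point or more between identical tapes would arise in about 43%, 26% and 17% of trials with 10, 20 and 30 subjects. At 20 subjects the figure runs from 35% to 15% over the correlations tried. The design reading is a firm inference, not a stated fact. Averaging does not bias complete data. The defect is the missing uncertainty, together with exposure to unequal sets of subjects if strips are lost. Because both primary outcomes are affected and the remedy is cheap, it should be corrected before the scores are examined.

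**What to change.** Change the SAP as follows.

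1. **Groups.** Define them as tape by heat condition, and do not pool heated and unheated arms.
2. **Primary outcomes.** For each subject, within each heat condition, compute Thermotape minus Tegaderm and Thermotape minus Kind. Report the mean paired difference with a 95% confidence interval. The subject is the unit, not the strip. Keep the averages as description.
3. **Primary contrasts.** Name them in advance, and say whether heated Thermotape against unheated comparators is one of them, since the Protocol's Background suggests that comparison. Put the remaining contrasts in a fixed order or adjust for their number.
4. **Missing strips.** State how many subjects contribute to each contrast, and how a lost strip, or one taken off with the silicone remover, enters the analysis.
5. **Sensitivity analysis.** A mixed model with a subject random effect may be added. It differs from the paired analysis in its assumptions and in how it handles missing values. Heat is always on the left arm, so its main effect cannot be separated from side. The same limit applies to any contrast of heated with unheated strips.
6. **Secondary outcomes.** For cells, average the five images within each strip first; for cells and hairs, use a paired method suited to counts. For TEWL, analyse taped minus untaped differences.

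The cost is SAP wording and somewhat more analysis work. No new data or subjects are needed.
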